3.2. Study Setting

The study was conducted in the General (Polivalent) Intensive Care Unit (ICU) of the Hospital Universitario Central de Asturias (HUCA), a major tertiary public hospital in Oviedo, Spain. HUCA is a modern, highly specialized center with advanced technological infrastructure, extensive ICU capacity, and multidisciplinary teams experienced in managing severe, complex critical illness. The polivalent ICU includes 44 beds distributed across general critical care and neuro-trauma units and provides comprehensive monitoring and life support for patients with multiorgan failure, high-risk postoperative complications, severe trauma, and complex infectious and medical conditions.

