3.3. Population and Sample

3.3.1. Study Subjects

Inclusion Criteria:

- Adults aged 18 years or older.
- Admission to HUCA's polivalent ICU for at least 24 hours.
- Intubated and receiving invasive mechanical ventilation.
- Presence of an arterial catheter and/or central venous catheter.
- Sedation level between BIS 40–60 or an equivalent level on the RASS scale (–3 to –4).
- Absence of pain at baseline and during the intervention, defined as a CPOT score of 0.
- No prior exposure to music therapy or similar interventions during the current hospital stay.
- Informed consent obtained from the patient's legally authorized representative within 72 hours of presentation.

Exclusion Criteria:

- Severe neurological disease or injury incompatible with study participation.
- Severe psychiatric illness such as psychosis or schizophrenia.
- Suspected or confirmed drug or alcohol intoxication, overdose, withdrawal, or abstinence.
- Hearing impairment that limits perception of the auditory intervention.
- Cranial injuries preventing safe placement of headphones.
- Limitation of therapeutic effort, expected death within 24 hours, or confirmed brain death.
- Current treatment with systemic corticosteroids.
- Requirement for vasoactive drugs above 0.1 mcg/kg/min.
- Refusal by the responsible attending physician.

Sample Size:

Using a pilot sample of 40 patients, a between-group difference of 1.32 units in serum cortisol and standard deviations of 2.86 (control) and 1.59 (intervention) were assumed. With 80% power and $\alpha = 0.05$, 50 subjects per group were required. After adjusting for a potential 20% loss rate, the final sample size required was 63 patients per group (126 total).

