3.6. Variables

Physiological variables were recorded every 10 minutes during the intervention.

Demographic and Clinical Variables:

- Age, sex, primary diagnosis at ICU admission.
- APACHE II severity score.
- Days on invasive mechanical ventilation at the time of intervention.
- Ventilatory mode and parameters, including FiO₂.
- Sedatives, analgesics, and neuromuscular blockers, with dose and infusion rate.

Physiological Parameters:

- Systolic and diastolic arterial blood pressure measured via arterial catheter.
- Heart rate via continuous ECG monitoring.
- Respiratory rate from the ventilator.
- Oxygen saturation (SpO₂).
- Level of sedation measured by BIS or RASS.

Biomarkers:

- Serum cortisol (primary biomarker), measured immediately before and after the intervention via arterial line.

- Serum prolactin and interleukin-6 (IL-6), measured at the same time points.

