3.8. Statistical Analysis

Analyses followed an intention-to-treat approach, with per-protocol sensitivity analyses. Continuous variables were summarized using mean \pm SD or median [IQR]; categorical variables using frequency and percentage.

Baseline differences were analyzed using Student's t-test or Mann–Whitney U test for continuous variables and chi-square or Fisher's exact test for categorical variables.

Primary analysis focused on the change in serum cortisol using linear mixed-effects models with fixed effects for group, time, and group \times time interaction, and random intercepts for subjects. Prolactin and IL-6 were analyzed similarly as key secondary outcomes. Non-parametric tests, including the Friedman test and Dunn post-hoc tests, were applied where model assumptions were violated.

Physiological trajectories were analyzed using repeated-measures mixed models incorporating the 10-minute time intervals.

Correlations were assessed using Pearson or Spearman coefficients. Multiple comparisons for secondary outcomes were controlled using the false discovery rate when necessary.

The significance threshold was 0.05. Analyses were performed using R version 4.4.3.

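### The plan names no analysis scale for prolactin and IL-6; if a marker is strongly right-skewed with proportional changes, the raw-scale model loses power and the named fallback does not test group × time

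*Combined protocol and SAP*

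**What the plan says.** Section 3.8 describes the cortisol analysis as "Primary analysis focused on the change in serum cortisol using linear mixed-effects models with fixed effects for group, time, and group" × time, with a random intercept per subject. It extends this to the other two biomarkers in one sentence: "Prolactin and IL-6 were analyzed similarly as key secondary outcomes". The next sentence gives the fallback: "Non-parametric tests, including the Friedman test and Dunn post-hoc tests, were applied where model assumptions were violated". No criterion for a violation is given. Section 3.8 allows medians and IQRs, but only as descriptive summaries.

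The biomarkers have one sample before and one after the session. Section 3.6 lists "Serum prolactin and interleukin-6 (IL-6), measured at the same time points" as cortisol. Cortisol was planned in concentration units: in section 3.3.1, "a between-group difference of 1.32 units in serum cortisol and standard deviations of 2.86 (control) and 1.59 (intervention) were assumed". No distribution, SD, expected effect or power is given for prolactin or IL-6. Section 3.2 describes a unit that treats "patients with multiorgan failure, high-risk postoperative complications, severe trauma, and complex infectious and medical conditions". The eligibility criteria set no limit on baseline IL-6 or prolactin.

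**The concern.** Cortisol is planned in raw units and its model is carried over without a transformation, so a reader would take prolactin and IL-6 to be analysed in raw units too. With one value before and one after, the group × time term then compares the mean absolute change between arms.

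If patients respond in proportion to their level, the same percentage change is a small number in a patient with a low baseline and a large one in a patient with a high baseline. The patients with the highest values then set both the estimate and its standard error. At stake are the power and the interpretability of the only two outcomes that the plan calls key secondary.

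The fallback matters equally. A skewed marker is the case in which it would be used, so it has to answer the same randomised question as the model it replaces.

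**Working it through.** **1. The plan's own figure (cortisol only).** Pooled SD = √[(2.86² + 1.59²)/2] = 2.314. By the normal approximation, n = 2 × (1.960 + 0.842)² × 2.314² / 1.32² = 48.2, so 49 per arm. The noncentral t gives 50 (power 0.806; 0.798 at 49). Then 50/0.80 = 62.5, so 63. The stated 50 and 63 per group reproduce. There is no corresponding figure for prolactin or IL-6.

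**2. What the model tests.** For complete pairs at two times, the group × time test equals a two-sample t-test on post minus pre.

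**3. Hand approximation.** Let the baseline X be log-normal with ln-SD *s*. Let the log change have SD σ in each arm and a between-arm difference δ. For small changes the raw change is about X × (log change). Its standardised effect is (δ/σ) × E[X]/√E[X²] = (δ/σ) × exp(−*s*²/2). Log-scale power of 80% corresponds to a test statistic centred at 2.802. On the raw scale:
- *s* = 0.3: 2.802 × 0.956 = 2.68, power about 76%.
- *s* = 0.5: 2.802 × 0.882 = 2.47, power about 70%.

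For larger *s* the normal approximation is poor, so simulation is used.

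**4. Simulation.** All inputs here are assumptions. The true ratio was set to give about 80% power on the log scale.
- Model A: ln-SD refers to the baseline value, with an independent log change of SD 0.2–0.4 and 50 per arm. The true ratios were 0.893 to 0.797.
- Model B: ln-SD refers to a stable patient level, with independent log error of SD 0.15 or 0.3 at each time and 50 or 63 per arm.

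| Between-patient ln-SD | Raw power, A | Raw power, B | Share of sum of squares from the five most extreme patients (B) |
|---|---|---|---|
| 0.3 | about 75–78% | 68–73% | 30–37% |
| 0.5 | about 70% | 62–66% | 38–44% |
| 1.0 | about 45% | 39–43% | 63–67% |
| 1.5 | about 25% | 21–23% | 81–83% |
| 2.0 | about 13% | 12–13% | 91% |

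Type I error of the raw test was about 4–5% up to ln-SD 1.0 and about 2–3% at 2.0.

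**5. Would the fallback be triggered?** The plan names no check. A Shapiro–Wilk test on the residuals of the change rejects in about 99% of trials at ln-SD 0.75 and in essentially all at 1.0 and above.

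**6. What the fallback tests.** With two times, Friedman's statistic within an arm of n patients, k of whom rise, is (2k − n)²/n. This is a sign test of pre against post. It was simulated with n = 63, ln-SD 1.0, log error SD 0.2 at each time, and a drift common to both arms, hence no treatment effect. It was significant in the music arm in 18%, 56% and 90% of trials for log drifts of −0.05, −0.10 and −0.15. It therefore does not stand in for group × time.

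**7. A between-group alternative.** A Mann–Whitney test on raw change keeps about 57–73% power over ln-SD 0.3 to 2.0. The plan does not name it for this comparison.

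**8. Reversed assumption.** With a log-normal baseline but additive effects and errors, raw power stays near 80%. Log-scale power falls to roughly 60% at ln-SD 0.5 and roughly 40% at 1.0.

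**The case against.** The strongest reply is that the plan already provides for skew. The large losses occur where almost any residual check would fail, so the 45% and 25% figures describe a model that the plan says it would leave. The fallback sentence also introduces its tests with the word including, so a between-group rank test is not ruled out. The first part stands: in the severe cases the raw model would probably not be the final analysis. The second part helps little. The only tests named do not address the randomised comparison, no suitable one is specified, and there is no trigger.

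Three further objections stand as limits:
- The amount of skew is not in the documents. Section 3.2 describes the unit, not the enrolled sample. Nothing in the documents supports strong skew for prolactin.
- The advantage of the log scale follows from assuming proportional effects and errors; additive ones reverse it.
- Section 3.3.1 powers cortisol only, so no planned power for these markers has been lost.

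A reader might also infer that a real effect would usually be missed, or that a few patients could produce a spurious significant result. Neither is supported. At ln-SD 0.3–0.5 raw power is still 62–78%, and the type I error does not exceed its nominal level beyond simulation error.

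**Conclusion.** The point holds in a conditional form. The plan does not state the scale for prolactin and IL-6. A reader might take it as settled that absolute concentrations are modelled, but that is inferred from silence and from the cortisol planning units.

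Under right skew with proportional changes, the loss against 80% on the log scale is small at ln-SD 0.3 (about 2 to 12 points), about 10 to 18 points at 0.5, and large at 1.0 (about 35 to 41 points) and 1.5 (about 55 to 59 points). For a skewed marker the plan as written leads either to a low-power raw model or to a within-arm test that misses the treatment comparison. This is a matter of power, influence and the question being tested, not of false positives from the raw model. The case is stronger for IL-6 than for prolactin, and the two should not be treated as equally affected. The change is worth making; confidence is medium, because the size rests on a dispersion that the documents do not give.

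**What to change.** In section 3.8, replace the sentence on prolactin and IL-6 with wording such as: IL-6 is analysed as natural-log concentration in the same mixed model; the effect is the music-to-control ratio of the geometric-mean post/pre ratios, with its 95% CI. Prolactin is analysed in the same way if it is right-skewed when assessed blind to group.

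Also:
- fix a rule for values below the assay limit;
- give the raw-scale results as a sensitivity analysis, which covers the possibility of additive effects;
- if a fallback is still wanted, replace Friedman/Dunn for these outcomes with a between-group rank test on change, and state what triggers it.

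Section 3.4 puts the end of data collection at 28 June 2025. If unblinded results have already been seen, label the log-scale analysis as post hoc and report it beside the analysis first carried out.

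The cost is a few sentences and a small change of code. The downside is that effects are reported as ratios rather than in concentration units. Cortisol can stay in its planning units.

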3.7.1. Randomization and Allocation

Participants were randomized to the music intervention group or the control group (quiet rest without headphones) using a computer-generated randomization list. The principal investigator remained unaware of allocation until consent was obtained.

Blinding included participants (sedated), bedside care providers, and laboratory personnel analyzing biomarker samples.

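### The only named fallback for the biomarker models, Friedman with Dunn post-hoc tests, has no specified music-versus-control contrast and no defined trigger

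*Combined protocol and SAP*

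**What the plan says.** Section 3.8 analyses the change in cortisol with "linear mixed-effects models with fixed effects for group, time, and group \times time interaction, and random intercepts for subjects", and treats prolactin and IL-6 in the same way. The group-by-time term carries the comparison of music with control.

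The same paragraph then gives the fallback: "Non-parametric tests, including the Friedman test and Dunn post-hoc tests, were applied where model assumptions were violated". It does not say which assumption is meant, how it is checked, whether Friedman is run within each arm or on all patients together, or what Dunn's test compares.

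Section 3.6 gives the sampling scheme: "Serum cortisol (primary biomarker), measured immediately before and after the intervention via arterial line". The other two biomarkers share those two time points. Section 3.7.1 describes two separately randomised arms.

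The only rank test in the plan that compares the arms is confined to baseline: "Baseline differences were analyzed using Student's t-test or Mann–Whitney U test for continuous variables".

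**The concern.** Friedman's test ranks the time points within each patient. It asks whether values moved over time and has no group or group-by-time term. With one sample before and one after, it reduces to counting how many patients rose and how many fell. A post-hoc test after it has no further pair of time points to separate.

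If the fallback is used in this way, the question changes from whether cortisol moved more with music to whether it moved during the hour. Two errors become possible. A real difference between arms can be missed when the arms move in opposite directions. A movement shared by both arms can also be read as an effect of music, if one arm reaches significance and the other does not. Section 3.7.2 cites circadian cortisol patterns when it fixes the session time, so a shared movement is plausible, although the plan gives neither its size nor its direction. The rule covers the primary outcome and both key secondary biomarkers.

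**Working it through.** **Inputs.** Section 3.3.1 gives "a between-group difference of 1.32 units in serum cortisol" and states that "standard deviations of 2.86 (control) and 1.59 (intervention) were assumed", with 80% power, alpha 0.05, 50 per group, and 63 per group after 20% loss. The plan does not say whether the SDs are of change or of single values. I take them as SDs of change and take changes as normal.

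**1. The plan's own figure.** The sum of variances is 2.86² + 1.59² = 8.180 + 2.528 = 10.708. With the normal approximation, n = (1.960 + 0.842)² × 10.708 / 1.32² = 7.849 × 10.708 / 1.742 = 48.2, so 49. With the t distribution, 49 gives 79.8% power and 50 gives 80.6%. Hence 50, and 50/0.80 = 62.5, so 63. The sample size reproduces.

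**2. Friedman with two time points.** The statistic becomes (number rising − number falling)² / n on 1 degree of freedom, which is the sign test. Arm does not enter it. Ranges below run from the exact sign test to the chi-square form.

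**3. A true difference of 1.32, assumed to split as +0.66 (control) and −0.66 (music), 50 per arm.**
- Probability that a control patient falls: Φ(−0.66/2.86) = Φ(−0.231) = 0.409.
- Probability that a music patient falls: Φ(0.66/1.59) = Φ(0.415) = 0.661.
- Share falling overall: (0.409 + 0.661)/2 = 0.535, close to the null value of 0.5.

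Share of simulated trials that are significant:

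| Test | Significant |
|---|---|
| Pooled Friedman | 7-11% |
| Mann-Whitney on change | 78% |
| Welch on change | 80% |
| Equal-variance t on change | 80% |

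With complete data, the last row is equivalent to the group-by-time test.

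**4. No music effect, both arms falling by an assumed 0.66, 50 per arm.**
- Probability of a fall: control Φ(0.231) = 0.591; music 0.661. The mean change is the same, but the smaller music SD makes the direction more consistent.
- Friedman within each arm, chi-square form: control significant in 29.2%, music in 68.2%. Significant in music only: 0.682 × (1 − 0.292) = 48%.
- Exact form: 20.0% and 57.1%, giving 0.571 × (1 − 0.200) = 46%.
- t and Welch on change reject in about 5%, Mann-Whitney in 5-6%.

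**5. Does the SD inequality endanger the planned test?** The SD ratio is 2.86/1.59 = 1.80 and the variance ratio 3.24. With equal arms the pooled and Welch standard errors coincide: √(10.708/50) = 0.463. Only the degrees of freedom differ, 98 against about 77. With no group difference, the group-by-time test rejects in 4.9-5.3% of simulated trials.

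**6. Cost of a between-group rank test.** Power for 1.32 is 78% against 80% at 50 per arm, and 87% against 89% at 63 per arm.

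**The case against.** Four points can be made for the plan.

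- **The primary model is right.** The group-by-time term is the correct contrast, and the defect bites only if the fallback is used. This stands, and it limits the severity.
- **The fallback is not strictly confined to time comparisons.** Dunn's test ordinarily compares independent groups, so it could compare the arms after the session or on change. The word including also leaves room for other tests. A reader might infer that neither named test can compare music with control. That is strictly true of Friedman only. For Dunn the fault is that the plan does not say what is compared, which leaves the contrast to be chosen after the data are seen.
- **Nothing shows that the fallback was likely to be used.** A reader might infer likelihood from the unequal planning SDs. If those SDs were true, a Brown-Forsythe check would fail in about 95% of trials at 50 per arm. But the documents mention no such check and do not make unequal variance a trigger. The SDs come from a pilot of 40 patients and say nothing about skewness. Step 5 shows that with equal arms the inequality hardly affects the planned test.
- **A significant pooled Friedman under shared drift is not a false positive for music.** In the scenario of step 4 it occurs in 67-74% of trials, but there the test correctly detects the drift that was put in. The figure relevant to a claim about music is significance in one arm only, and it requires separate testing by arm, which the plan does not state.

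The split in step 3 is also unfavourable to Friedman. If control stays flat and music falls by 1.32, pooled Friedman is significant in 83-88% of trials. It is then still reporting a change over time, not a difference between arms.

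**Conclusion.** The point holds in this form: section 3.8 names a fallback that specifies no between-group contrast of change and has no defined trigger. If Friedman is used as named, music against control is not tested for the biomarker concerned.

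In the illustrations, detection of a true 1.32 difference drops from about 80% to 7-11% when the arms move in opposite directions. A misleading result in music only appears in about 46-48% of trials under a shared fall of 0.66 with separate testing by arm. Both sizes rest on assumed movements, normal changes, and the stated SDs being SDs of change. That Friedman lacks a group term rests on none of these.

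The documents support no statement about how often the fallback was, or would be, used. Because the primary model contains the right contrast, this is a should-fix point.

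**What to change.** In section 3.8:

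- Keep the group-by-time mixed model as the primary analysis.
- Replace Friedman and Dunn with a between-group analysis of the before-to-after change. For non-normality, use Mann-Whitney or Brunner-Munzel on change; the latter also allows for unequal spread. For unequal variance, use Welch or a model with arm-specific variances.
- Report the rank-based test beside the primary result as a fixed sensitivity analysis for all three biomarkers, so that no assumption check decides which test is reported.
- State that no efficacy claim rests on within-arm tests or on a pooled test of time.

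Section 3.4 shows that data collection ended on 28 June 2025, so the change should be disclosed as a retrospective amendment. If Friedman or Dunn results already exist, label them as descriptions of change over time.

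The cost is a few sentences and a few lines of R, with no new data and no change to the sample size. The rank test gives up about 2 points of power; Welch or arm-specific variances give up almost none.

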3.9. Ethical Considerations and Funding

The study adhered to the Declaration of Helsinki, the Belmont Report, CIOMS Guidelines, and Spanish Organic Law 3/2018 on data protection. Ethics approval was obtained from the Ethics Committee of the Principality of Asturias (code 2022.537). The trial was registered at ClinicalTrials.gov (NCT06120660). Written informed consent was obtained from each legally authorized representative prior to participation. Confidentiality was ensured through coded identifiers and restricted data access.

Funding:

This study received no institutional funding from the University of Oviedo. Financial support was provided exclusively by the Spanish Society of Intensive and Coronary Care Nursing (SEEIUC) through the “SEEIUC Investiga” Grant 2023 (5th Edition), with a total amount of €4,000, awarded to the project “Efectos de la intervención musical en el estrés del paciente crítico.”
